7.5.1.3. Reporting Periods for Adverse Events and Serious Adverse Events

The safety reporting period for AEs is from study Day 1 (predose) through the EOT visit or 30 days after the last study treatment, whichever is later. The reporting period for SAEs is from study Day 1 (predose) through the EOT visit or 90 days after the last study treatment, whichever is later. Events will be recorded at each examination on the Adverse Event CRFs/worksheets. However, all study protocol-related AEs are to be recorded from the time of informed consent. All SAEs that occur after the safety reporting period and are considered study treatment-related in the opinion of the investigator should also be reported to the sponsor. The investigator will make every attempt to follow all patients with non-serious AEs for outcome.

The reporting timeframe for AEs meeting any serious criteria is described in Section 7.5.1.4.

SAEs will be followed until significant changes return to baseline, the event stabilizes (recovering/resolving) or is no longer considered clinically significant by the investigator, or the patient dies or withdraws consent. All non-serious AEs will be followed through the safety reporting period. Certain non-serious AEs of interest may be followed until resolution, return to baseline, or study closure, whichever comes first. In particular these include AEs of peripheral neuropathy in all patients.

7.5.1.4. Serious Adverse Events Require Immediate Reporting

Within 24 hours of observing or learning of an SAE, investigators are to report the event to the sponsor, regardless of the relationship of the event to the study treatment regimen.

For initial SAE reports, available case details are to be recorded on an SAE form. At a minimum, the following should be included:

- Patient number
- Date of event onset
- Description of the event
- Study treatment, if known

The completed SAE form and SAE Fax Cover Sheet are to be emailed or faxed to the sponsor's Drug Safety Department within 24 hours (see email or fax number specified on the SAE report form).

Relevant follow-up information is to be submitted to the sponsor as soon as it becomes available.

7.5.1.5. Sponsor Safety Reporting to Regulatory Authorities

Investigators are required to report all SAEs, including anticipated SAEs, to the sponsor (see Section 7.5.1.4).

The sponsor will report all SAEs, including SUSARs, to regulatory authorities as required per local legislation or regulatory reporting requirements.

In the US, endpoints that assess disease-related mortality or major morbidity, as well as other SAEs that are not study endpoints but are known consequences of the underlying disease or

condition that are anticipated to occur in the study population, should not be reported to the Food and Drug Administration (FDA) as individual IND safety reports per the final rule amending the IND safety reporting requirements under 21 CFR 312.32 and the FDA's guidance Safety Assessment for IND Safety Reporting Guidance for Industry (draft guidance December 2015).

In this study, the SAEs that do not require individual IND safety reports be submitted to the FDA are progression of the underlying cancer. These anticipated SAEs will be reviewed periodically by an SMC and Seagen Drug Safety Department. If upon review, an SAE is occurring at a higher rate than that which would be expected for the study population, then an IND safety report for the SAE will be submitted to the FDA.

7.5.1.6. Events of Clinical Interest

Selected non-serious and serious AEs are also known as Events of Clinical Interest (ECIs) and must be reported to the sponsor.

For the time period beginning when the consent form is signed until treatment allocation, any ECI, or follow-up to an ECI, which occurs in any patient, must be reported within 24 hours to the sponsor if it causes the patient to be excluded from the trial, or is the result of a protocol-specified intervention, including but not limited to washout or discontinuation of usual therapy, diet, or a procedure.

For the time period beginning at treatment allocation through 30 days following the last study drug dose, any ECI, or follow-up to an ECI, whether or not related to the sponsor's product, must be reported within 24 hours to the sponsor, either by electronic media or paper. Electronic reporting procedures can be found in the EDC data entry guidelines.

ECIs for this trial include:

- An overdose of either study product, as defined in Sections 5.2.4 and 5.3.4, and is not associated with clinical symptoms or abnormal laboratory results.
- An elevated AST or ALT lab value that is ≥3x ULN, and an elevated total bilirubin lab value that is ≥2x ULN and, at the same time, an alkaline phosphatase lab value that is <2x ULN, as determined by way of protocol-specified laboratory testing, or unscheduled laboratory testing. *

*Note: These criteria are based upon available regulatory guidance documents. The purpose of the criteria is to specify a threshold of abnormal hepatic tests that may require an additional evaluation for an underlying etiology. The trial site guidance for assessment and follow-up of these criteria can be found in the Investigator Trial File Binder (or equivalent).

7.5.2. Vital Signs

Vital signs include measurements of respiratory rate, pulse rate, and systolic and diastolic blood pressure while the patient is in a seated position, pulse oximetry, and temperature.

Vital signs should be measured within 60 minutes prior to LV infusion, within 60 minutes prior to pembrolizumab infusion (Day 1 only), within 2 hours of ending each infusion, and during

infusion/s as clinically indicated. In addition, vital signs should be measured at other specified time points as outlined in the schedule of activities (see Appendix A and Appendix C).

7.5.3. Clinical Laboratory Tests

For Part A and Part B Cohort 1, samples will be drawn for central and local labs. Local laboratory testing will include blood glucose and other institutional standard tests for evaluating safety and making clinical decisions. The following laboratory assessments will be performed by a central laboratory during the course of the study (schedule in Appendix A and Appendix C):

- The serum chemistry panel is to include the following tests: albumin, alkaline phosphatase, ALT, AST, blood urea nitrogen, calcium, creatinine, chloride, blood glucose, phosphorus, potassium, sodium, total bilirubin, amylase, lipase, and uric acid.
- The CBC with differential is to include the following tests: WBC count with five-part differential (neutrophils, lymphocytes, monocytes, eosinophils, and basophils), RBC count, absolute neutrophil count, platelet count, hemoglobin, and hematocrit.
- Tumor markers (if already being performed per the site's standard of care) such as CEA, CA15-3, and CA27-29

For Part A and Part B Cohort 1, the following laboratory assessments will be performed only by local laboratories at scheduled time points during the course of the study (see Appendix A):

- HbA1c: if HbA1c is elevated during screening, a repeat HbA1c must be obtained
- Fasting blood glucose is only required at screening (other scheduled tests do not require
 the patient to fast). If fasting blood glucose is elevated during screening, a repeat fasting
 blood glucose must be obtained.
- Coagulation parameters: PT, PTT, aPTT, and INR
- Hepatitis B virus (HBV) serology: HBsAg and HBcAb; HBV DNA test for patients with a negative HBsAg test and a positive total HBcAb.
- Hepatitis C viral load by PCR.
- Thyroid function tests, including TSH, T3 or free T3, and free T4.
- For patients of childbearing potential, a serum or urine β-hCG pregnancy test with sensitivity of at least 25 mIU/mL.

For Part B Cohort 2 and Parts C and D, all laboratory assessments will be performed locally and results are to be submitted to the central laboratory (with the exception of pregnancy testing, which does not need to be submitted to the central laboratory).

Refer to the Laboratory Manual for information on collection, processing, storage, and shipment of samples.

7.5.4. Physical Examination

Physical examinations should include assessments of the following body parts/systems: abdomen, extremities, head, heart, lungs, neck, and neurological. For adult patients only, measurements of height obtained within the prior 12 months may be utilized.

7.5.5. Pregnancy Testing

For women of childbearing potential, a serum or urine β -hCG pregnancy test with sensitivity of at least 25 mIU/mL will be performed at baseline, within 3 days prior to each Day 1 study drug dose at each cycle, and at the EOT visit. A negative pregnancy result is required before the patient may receive study drug. Pregnancy tests may also be repeated as requested per Institutional Review Board (IRB)/ Independent Ethics Committee (IEC) or if required by local regulations.

7.6. Appropriateness of Measurements

The safety measures that will be used in this trial are considered standard procedures for evaluating the potential adverse effects of study medications.

Immunogenicity is commonly assessed for biologics; therefore, standard tests may be performed to detect the possible presence of specific antibodies to LV. PK assessments are also common in clinical studies to help characterize dose-exposure-response relationships.

Amendment 11: 19-Oct-2023

Page 83 of 152

8. DATA QUALITY CONTROL AND QUALITY ASSURANCE

8.1. Site Training and Monitoring Procedures

A study manual with instructions for study compliance and CRF completion will be provided. Prior to the enrollment of patients at the site, Seagen or its designated clinical and medical personnel will review the following items with the investigator and clinic staff:

- The protocol, study objectives, eligibility requirements, study procedures, registration and withdrawal processes
- Current IB/package insert
- Recording and reporting AEs and SAEs
- Enrollment goals and study timelines
- The CRF completion process and source documentation requirements
- Monitoring requirements
- IRB/IEC review and approval process
- Informed consent process
- Good Clinical Practice guidelines and related regulatory documentation requirements
- Key study team roles and responsibilities
- Investigational product storage, accountability, labeling, dispensing, and record keeping
- Patient coding
- Study samples/specimen collection, handling, and shipping
- Protocol compliance
- Clinical study record keeping, document retention, and administrative requirements

Monitoring visits will occur periodically, with frequency dependent on the rate of enrollment and workload at each site. During monitoring visits, the Seagen representative will review regulatory documentation, CRFs, source documentation, and investigational product storage, preparation, and accountability. The CRFs will be reviewed for completeness, adherence to the provided guidelines, and accuracy compared to the source documents. The investigators must ensure that the monitor is allowed to inspect all source documents pertinent to study patients and must cooperate with the monitor to ensure that any problems noted in the course of the trial are resolved. The investigator must maintain a comprehensive and centralized filing system of all study-related documentation that is suitable for inspection by Seagen or its designated monitors and by quality assurance auditors, or representatives of regulatory authorities.

8.2. Data Management Procedures

Seagen will provide CRF Completion Guidelines for electronic CRF (eCRF) data entry. Study specific data management procedures will be maintained in the data management plan. Queries resulting from edit checks and/or data verification procedures will be posted electronically in the eCRF.

Amendment 11: 19-Oct-2023

Page 84 of 152

8.3. Access to Source Data

The investigator will permit the sponsor's representatives to monitor the study as frequently as the sponsor deems necessary to determine that protocol adherence and data recording are satisfactory. Appropriate measures to protect patient confidentiality are to be employed during monitoring. The CRFs and related source documents will be reviewed in detail by the monitor at each site visit. Original source documents or certified copies are needed for review. This review includes inspection of data acquired as a requirement for participation in this study and other medical records as required to confirm that the information contained in the CRFs, such as disease assessments, AEs, and concomitant medications, is complete and correct. Other study records, such as correspondence with the sponsor and the IRB/IEC and screening and drug accountability logs will also be inspected. All source data and study records must also be available for inspection by representatives of regulatory authorities or audits by sponsor auditors.

8.4. Accuracy and Reliability of Data

Steps to be taken to assure the accuracy and reliability of data include:

- The selection of qualified investigators and appropriate study centers.
- Review of protocol procedures with the investigators and associated personnel prior to the study.
- Periodic monitoring visits by the designated monitor(s).
- CRFs will be reviewed for accuracy and completeness by the designated monitor(s)
 during monitoring visits to the study centers. Any discrepancies will be resolved with the
 investigator or designees as appropriate.

8.5. Quality Assurance Procedures

The Research and Development Quality (RDQ) group or its designee may conduct audits at the clinical site or other study-related facilities and organizations. Audit reports will be retained by the RDQ group of Seagen as part of the written record.

8.6. Data Handling and Record Keeping

8.6.1. Data Handling

It is the investigator's responsibility to ensure the accuracy, completeness, legibility, and timeliness of the data reported to the sponsor in the CRFs and in all required reports. Data reported on the CRF that is derived from source documents should be consistent with the source documents or the discrepancies should be explained.

Any change or correction to a CRF will be maintained in an audit trail within the EDC system. Data changes may only be made by those individuals so authorized. The investigator should retain records of the changes and corrections, written and/or electronic.

8.6.2. Investigator Record Retention

The investigator shall retain study drug disposition records and all source documentation (such as original ECG tracings, laboratory reports, inpatient or office patient records) for the maximum period required by the country and institution in which the study will be conducted, or for the

period specified by Seagen, whichever is longer. The investigator must contact Seagen prior to destroying any records associated with the study. If the investigator withdraws from the study (due to relocation, retirement, etc.), the records shall be transferred to a mutually agreed upon designee, such as another investigator or IRB/IEC. Notice of such transfer will be provided in writing to Seagen.

Amendment 11: 19-Oct-2023

Page 86 of 152

DATA ANALYSIS METHODS

9.1. Determination of Sample Size

Approximately 189-211 patients will be enrolled in this study, of which approximately 12-24 patients will be enrolled in Part A, approximately 73 patients will be enrolled in Part B (approximately 48 in Cohort 1 and approximately 25 in Cohort 2), approximately 64 patients will be enrolled in Part C, and approximately 40 patients will be enrolled in Part D.

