Approximately 189–211 patients are expected to be enrolled, including approximately 12–24 patients enrolled in Part A (LV dose de-escalation), approximately 73 patients in Part B (expansion), approximately 64 patients in Part C (LV weekly [q1wk] dosing), and approximately 40 patients in Part D (LV Day 1, Day 8 in 21-day cycle dosing). In Part B, approximately 48 patients will be enrolled at the maximum administered dose (MAD) of LV 2.5 mg/kg and approximately 25 patients will be enrolled at the lower dose of 2.0 mg/kg LV in combination with pembrolizumab. In Part C, approximately 64 patients, including approximately 60 patients in the expansion cohort, will be enrolled and will receive LV 1.0 or 1.25 mg/kg on Day 1, Day 8, and Day 15 in every 21-day cycle, in combination with pembrolizumab administered on Day 1 of every cycle. In Part D, approximately 40 patients will be enrolled and will receive LV 1.5 mg/kg on Day 1 and Day 8 (off Day 15) in every 21-day cycle, not to exceed 200 mg per infusion, in combination with pembrolizumab administered on Day 1 of every cycle.

Study Design

This is a single-arm, open-label, multicenter trial designed to assess the safety and efficacy of LV in combination with pembrolizumab for the treatment of LA/M TNBC. Patients will be enrolled into Part A, Part B, Part C, and Part D sequentially. Patients will enroll in Part B Cohort 1 and Part B Cohort 2 sequentially.

In Part A, patients will receive a dose of LV 2.5 mg/kg as an intravenous (IV) infusion over approximately 30 minutes followed by pembrolizumab 200 mg IV over approximately 30 minutes on Day 1 of each 21-day cycle. In consultation with the sponsor, eligible patients already on treatment prior to Amendment 2, may have their maximum weight cap per infusion increased to 100 kg or remain at 80 kg, if they are receiving benefit (complete response [CR], partial response [PR], or stable disease [SD]). Patients receiving >200 mg LV per infusion are required to be administered prophylactic granulocyte-colony stimulating factor (G-CSF). Dosing may be descalated based upon the frequency of dose-limiting-toxicities (DLTs) in Cycle 1.

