The safety analysis set will include patients treated with any amount of LV or pembrolizumab. This is also referred to as the all treated patients set for some efficacy analyses. The DLT-evaluable (DE) analysis set includes all patients in the safety analysis set who either (1) experience a DLT or (2) receive at least 75% of intended LV and pembrolizumab doses and are followed for the full DLT evaluation period (Cycle 1). The DE patient set will be the primary population for Part A, and will be used for the determination of the MAD for Part B. The all treated analysis set includes all enrolled patients who receive any amount of LV or pembrolizumab and will be the primary set for efficacy analysis. The efficacy-evaluable (EE) set includes all patients in the all treated analysis set who have both a baseline and at least 1 evaluable post-baseline disease assessment according to the RECIST v1.1 and iRECIST criteria, or per investigator determination of clinical disease progression.

Exact 95% confidence intervals (CIs) for ORR and DCR will be provided. DOR, PFS, and OS will be analyzed using the Kaplan-Meier method. The primary analyses of efficacy endpoints will be performed for all treated patients analysis set. All safety analyses will be based on the safety analysis set.

Approximately 60 patients total are expected to be enrolled at the MAD assuming that Part A will enroll 12 patients at the MAD and Part B Cohort 1 will enroll approximately 48 patients, at the MAD. Based on the SGNLVA-001 Phase 1 study, it is estimated that about 70% of patients are LIV-1-positive. Thus, approximately 42 LIV-1-positive patients in total will be enrolled at the MAD. Assuming the observed ORR is between 50% and 70%, the widths of 2-sided 95% CIs are summarized below.

Confirmed ORR	Expected width of 95% CI on LIV-1-positive patients (N=42)	Expected width of 95% CI on all patients at the MAD (N=60)
50%	±16%	±13%
60%	±16%	±13%
70%	±15%	±12%

Part B Cohort 2 will enroll approximately 25 patients at 2.0 mg/kg. With the patients in Part A enrolled at 2.0 mg/kg, approximately 30 patients in total will be enrolled at 2.0 mg/kg. Assuming the observed ORR is between 50-70%, the widths of 2-sided 95% CIs are summarized as below.

	Expected width of 95% CI on all patients at 2.0 mg/kg		
Confirmed ORR	(N=30)		
50%	±18%		
60%	±18%		
70%	±16%		

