9.1.2. Part B

Once the MAD has been identified in Part A, patients will be enrolled in Part B Cohort 1 at the MAD. Approximately 42 LIV-1-positive patients in total will be enrolled at the MAD. Based on the SGNLVA-001 phase 1 study, it is estimated that about 70% of patients are LIV-1-positive. Approximately 60 patients are expected to be enrolled at the MAD, assuming that Part A will enroll 12 patients at the MAD and approximately 48 patients are expected to be enrolled in Part B Cohort 1 at the MAD. Assuming the observed ORR is between 50% and 70%, the widths of 2-sided 95% confidence intervals (CIs) are summarized as below.

Amendment 11: 19-Oct-2023

Page 87 of 152

Confirmed ORR	Expected width of 95% CI on LIV-1-positive patients (N=42)	Expected width of 95% CI on all patients at the MAD (N=60)
50%	±16%	±13%
60%	±16%	±13%
70%	±15%	±12%

Part B Cohort 2 will enroll approximately 25 patients at 2.0 mg/kg. With the patients in Part A enrolled at 2.0 mg/kg, approximately 30 patients in total will be enrolled at 2.0 mg/kg. Assuming the observed ORR is between 50% to 70%, the widths of 2-sided 95% CIs are summarized as below

Confirmed ORR	Expected width of 95% CI on all patients at 2.0 mg/kg (N=30)
50%	±18%
60%	±18%
70%	±16%

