9.3.6.1. Primary Efficacy Analyses

The primary efficacy endpoint is the confirmed ORR per investigator assessment. The ORR is defined as the proportion of patients with confirmed CR or PR according to RECIST v1.1. Patients who do not have at least 2 post-baseline response assessments (initial response and confirmation scan) will be counted as non-responders. The observed ORR and its corresponding exact 2-sided 95% CI will be summarized using the Clopper-Pearson method (Clopper 1934).

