#### 5 STATISTICAL CONSIDERATIONS

# 5.1 General Principles

Descriptive statistics (mean, median, standard deviation, minimum, and maximum) will be summarize continuous variables, Frequencies and percentages will be used to summarize categorical variables. The two-sided 95% exact confidence interval using Clopper-Pearson methodology (Clopper 1934) will be calculated for the response rates where applicable (e.g., ORR).

The median survival time will be estimated using the Kaplan-Meier method; the associated 95% confidence interval (CI) will be calculated based on the complementary log-log transformation (Collett 1994).

Unless otherwise specified, data are to be summarized by dose level and overall. DLT analysis will only include patients in Part A and Part C dose finding part.

Any analysis not described in this plan will be considered exploratory, and will be documented in the clinical study report (CSR) as a post hoc analysis or a change to the planned analysis.

To comply with regulatory electronic submission guidelines, listings of all clinical data will be submitted as electronic data sets. To facilitate data review for the study report, only pertinent data listings will be created and attached to the appendix of the CSR. All statistical tables, listings, and figures will be produced using SAS, version 9.3 or more recent. Other statistical software, if used, will be described in the CSR.

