#### 5.2 Determination of Sample Size

Approximately 189–211 patients will be enrolled in this study, of which approximately 12–24 patients will be enrolled in Part A, approximately 73 patients will be enrolled in Part B (approximately 48 in Cohort 1 and approximately 25 in Cohort 2), and approximately 64 enrolled in Part C, and approximately 40 patients will be enrolled in Part D.

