#### 5.2.3 Part C

In Part C, it is estimated that approximately 4 to 12 patients (assuming evaluation of 2 dose levels) will be treated in dose escalation. Operating characteristics of the dose escalation design, including the average number of patients allocated to each dose across a variety of toxicity scenarios, are presented in the simulation report (Error! Reference source not found.).

Up to approximately 64 patients may be enrolled across the dose escalation and expansion cohorts in Part C. In the case that both dose levels go to expansion, approximately 12 patients will be enrolled in each dose level (assuming 2 patients in each of the dose escalation cohort of 1.0 and 1.25 mg/kg and 60 patients in the expansion cohort).

The table below summarizes the 2-sided 95% exact confidence intervals among 62 patients at 1.25 mg/kg (2 in dose escalation and 60 in dose expansion cohort) assuming the observed ORR is between 50% and 70%.

Study SGNLVA-002 Ladiratuzumab vedotin Statistical Analysis Plan Seagen, Inc. - Confidential 01-May-2024 Page 11 of 32

Number of confirmed Objective Response	Confirmed ORR	95% exact CI (N=62)	
31	50%	37%, 63%	
37	60%	46%, 72%	
43	69%	56%, 80%	

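### Three planning figures do not follow from the plan's own inputs: the 211 enrolment ceiling, the N=30 confidence-interval half-widths, and the SAP's 12 patients per Part C dose level

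*Protocol*

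**What the plan says.** **Total enrolment.** Protocol 9.1 states "Approximately 189-211 patients will be enrolled in this study", SAP 5.2 states "Approximately 189–211 patients will be enrolled in this study", and the synopsis states "Approximately 189–211 patients are expected to be enrolled". All three list the same components: Part A 12–24, Part B 73 (48 + 25), Part C 64, Part D 40.

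**Precision at 2.0 mg/kg.** Protocol 9.1.2, the synopsis and SAP 5.2.2 carry a table headed "Expected width of 95% CI on all patients at 2.0 mg/kg" for N=30. It gives ±18%, ±18% and ±16% at observed response rates of 50%, 60% and 70%, and names no interval method. The table just above it gives ±16/±16/±15% for N=42 and ±13/±13/±12% for N=60. For the analysis itself, Protocol 9.3.6.1 says: "The observed ORR and its corresponding exact 2-sided 95% CI will be summarized using the Clopper-Pearson method". SAP 5.1 names the same method for response rates: "The two-sided 95% exact confidence interval using Clopper-Pearson methodology".

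**Part C.** SAP 5.2.3 allows up to about 64 patients. It then says that, if both dose levels expand, "approximately 12 patients will be enrolled in each dose level". The parenthesis closing that sentence assumes 2 escalation patients at each of two doses plus 60 expansion patients. Protocol 9.1.3 has no 12-per-dose clause; it attaches the parenthesis to the 64-patient total and places all 60 expansion patients at 1.25 mg/kg.

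**The concern.** Each figure can be checked against inputs in the same sentence or section, and each fails.

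- The lower enrolment bound is the exact sum of the listed parts, so the upper bound should be too. It is not.
- The N=30 half-widths look small beside the N=42 and N=60 columns, which suggests a different method from the one planned for the primary efficacy endpoint.
- Twelve patients at each of two doses cannot equal 64.

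At stake are the headline sample size in both documents, the precision claimed for the confirmed response rate at 2.0 mg/kg, and a SAP statement of how many patients each Part C dose would have. A reader comparing achieved enrolment or precision with the plan would use the wrong reference values.

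**Working it through.** **1. Enrolment** (components from Protocol 9.1)

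- Lower bound: 12 + 73 + 64 + 40 = 189. This reproduces.
- Upper bound: 24 + 73 + 64 + 40 = 201, against 211 stated. The difference is 10, or 10/201 = 5%.
- Could a larger Part C explain it? Protocol 9.1.3 expects 4 to 12 escalation patients. With 12 of them plus 60 in expansion, Part C is 72 and the total is 24 + 73 + 72 + 40 = 209, still not 211.

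**2. Half-widths for a 95% interval**

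Wald half-width: 1.96 × √(p(1−p)/n). Clopper-Pearson half-width: (U − L)/2, where, for x responses in n, L is the 2.5% point of Beta(x, n−x+1) and U is the 97.5% point of Beta(x+1, n−x). For N=42 the nearest whole counts are 21, 25 and 29.

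| N | Responses | Stated ± | Exact ± | Wald ± |
|---|---|---|---|---|
| 42 | 21, 25, 29 | 16, 16, 15 | 15.8, 15.5, 14.7 | 15.1, 14.8, 13.9 |
| 60 | 30, 36, 42 | 13, 13, 12 | 13.2, 12.9, 12.2 | 12.6, 12.4, 11.6 |
| 30 | 15, 18, 21 | 18, 18, 16 | 18.7, 18.4, 17.3 | 17.9, 17.5, 16.4 |

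- N=42: only the exact column rounds to the stated values.
- N=60: the 60% row separates the methods. Exact 12.9 rounds to the stated 13; Wald 12.4 rounds to 12.
- N=30: only the Wald column rounds to the stated values. The exact intervals are 31.3–68.7%, 40.6–77.3% and 50.6–85.3%, giving ±19, ±18 and ±17 after rounding.
- Sensitivity to the approximate N: with 31 patients the exact half-width near 70% is 16.9 (22/31) or 17.35 (21/31), so ±16 fails there too. Near 50% it is 18.4, so ±19 applies to N=30 as labelled.

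**3. Part C in SAP 5.2.3**

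- Clause: 2 dose levels × 12 = 24.
- Parenthesis in the same sentence: 2 + 2 + 60 = 64, which agrees with the sentence before it.
- By inference only: the document history records 40 patients added to Part C, and 64 − 40 = 24, so the clause looks like text left from the smaller plan. The contradiction does not depend on this.

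**Figures that do reproduce**

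- Part A de-escalation, the probability of at least 2 DLTs in the first 6 patients, or fewer than 2 and then at least 4 in 12: 11.4% + 0.6% = 12.1% (unrounded sum) at a true rate of 10%, and 89.1% + 6.7% = 95.8% at 50%; stated 12% and 96%.
- Part C, N=62: 37.0–63.0, 46.4–71.9 and 56.3–80.4, as stated after rounding.
- Part D, N=40: 33.8–66.2, 43.3–75.1 and 53.5–83.4, as stated after rounding.
- Part D adverse-event detection: 1 − 0.95^40 = 87.1% and 1 − 0.90^40 = 98.5%; stated 87% and 99%.

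**The case against.** The enrolment sum and the Part C contradiction are hard to dispute. Calling the planned sizes approximate does not rescue 211, because the lower bound is exact and the one component range is already counted. The serious objections are these.

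- **The N=30 table is not labelled exact.** Its values are correct normal-approximation half-widths, while the Part C and Part D tables are explicitly labelled exact. That is fair: the fault is the mismatch with the planned method and with the adjacent columns, not a miscalculation. It shifts two rows by about 1 point and leaves the 60% row unchanged.
- **Nothing downstream depends on these figures.** There is no hypothesis test and no formal interim analysis, and the exact interval will be computed from the observed data whatever the table says. This stands and limits the importance of the point.
- **A symmetric ± does not describe an exact interval.** At 21/30 the limits lie 19.4 points below and 15.3 above the estimate. This is true, but the N=42 and N=60 columns use the same half-width format. Printing the limits, as the Part C and Part D tables do, would be better still.
- **The 64 for Part C may not be firm**, since more than 4 escalation patients are possible. Even so, 201 is what the listed parts give. If the sponsor changes a part, the total should change with it.

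**Conclusion.** The concern holds on all three counts.

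- The enrolment ceiling is overstated by 10 patients (5% of 201) in three places.
- The N=30 half-widths are not those of the planned Clopper-Pearson interval. They understate it by 0.7 points at 50% (18 against 18.7) and 1.3 points at 70% (16 against 17.3), also in three places.
- SAP 5.2.3 implies 24 patients and 64 patients in one sentence.

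The result assumes that the listed part sizes are the intended ones, which the exact lower bound supports, and that N is 30 as labelled. No analysis, decision rule or reported estimate is affected. The corrections should be made because the figures are the stated sample size and the stated precision for the primary efficacy endpoint.

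**What to change.** 1. In the synopsis, Protocol 9.1 and SAP 5.2, replace 211 with 201, after confirming that the part sizes are as listed.
2. In the synopsis, Protocol 9.1.2 and SAP 5.2.2, replace the N=30 values with ±19%, ±18% and ±17% and name the method. Preferably, print the exact limits alongside: 31–69%, 41–77% and 51–85%.
3. In SAP 5.2.3, delete the clause giving about 12 patients per dose level and attach its parenthesis to the 64-patient sentence, as Protocol 9.1.3 does. Do not substitute another per-dose number, because neither document plans a split of the expansion patients.

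The cost is text edits only. Two stated half-widths become about 1 point less favourable. If the documents can no longer be amended, the three corrections can be recorded in the study report.
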